10.3 KT framework/platform

A major component of the proposed project is to collect information that is appropriate to enable knowledge users to glean the information they need to inform new initiatives within their own organizations (i.e. knowledge-to-action).(91) The integrated (*iKT*) approach enhances the likelihood that the *Prehab* intervention will be implemented in the Canadian health care system and be sustainable over the long term. We have already taken the initial steps to implement an *iKT* approach to this application. Our intention of doing so was to include key stakeholders and potential knowledge users early in the process “to shape the research process by collaborating to determine the research questions, deciding on the methodology, being involved in data collection and tools development, interpreting the findings, and helping disseminate the research results”.(2) We have open relationships with the partners and key stakeholders needed to design and operate our study. Our ‘push’ efforts to link research to action will include patients/families (through shared decision-making efforts),(82)(83)(84) primary care providers, cardiac surgeons and cardiac rehab centres; while ‘pull’ efforts by our stakeholders will be enhanced by their involvement in the design and reporting of the study. Finally, we have included a solid evaluation of our efforts to link research to action (ref: Ellen M. WHO Knowledge Translation Framework for Ageing and Health. April 2012). By using an *iKT* approach

“The PREHAB Study” (Pre-operative Rehabilitation for reduction of Hospitalization After coronary Bypass and valvular surgery.)

and best practice evidence to inform a model of care for frail elderly persons needing cardiac surgery, the project will be able to influence the health system in a variety of ways.

10.4 Project engagement

Although we have already taken the initial steps to implement the *iKT* approach during the development of the grant application, once the project has begun we will convene a group of community stakeholders that include representatives from all the project sites, patients with higher levels of frailty who have previously undergone cardiac surgery and their family caregivers. Our intention of bringing these stakeholders together with the research team is to optimize the project intervention within the context of the patient experience prior to cardiac surgery, thereby facilitating ‘pull’ efforts (WHO 2012). Moreover, this group will identify ways to address the barriers that may arise as the *Prehab* intervention is implemented at each site; this effort is aided by the climate for research that exists in our context. This *iKT* approach will inform our work plan, ensuring that the voices and experiences of stakeholders, patients and families have been considered. These stakeholders will also serve as the steering committee to provide input to refine the *Prehab* approach.

“The PREHAB Study” (Pre-operative Rehabilitation for reduction of Hospitalization After coronary Bypass and valvular surgery.)

Tables

Table 1 - How the PREHAB Study fits in the Technology Evaluation Framework

	Exploratory	Efficacy	Effectiveness (current state)	Cost-effectiveness
Patients and Families	We have examined the effects of prolonged hospitalization and its impact on new mood disorders and reduced cardiac rehab (CR) activity (Horne et al., 2013).	
Low to High Tech:
 
 1. Implementation of a frailty screening protocol in elective cardiac surgery patients and determination of a clinically meaningful endpoint of patient care/healthy living 2. Performed a pilot RCT on pre-operative cardiac rehabilitation (“prehab”) on elective cardiac surgery patient to determine feasibility and safety. 	
Engage, Empower and Support:
 
We plan to hold focus group discussions to learn more about attitudes of the value of Prehab for the treatment of frail elderly patients. This will involve interaction with the patient and their families and determine methods to ensure shared decision making and post-operative healthy living & sustainable well-being
	
Health Care Professionals	Utilization of the Canadian Cardiovascular Critical Care (CANCARE) Society Network to identify the lack of peri-operative protocols for frail elderly persons and care of the cardiac surgery patient (Lamarche et al., 2012)	
Improving Outcomes:
 
We have identified Canadian centers capable of engaging in multicenter Prehab RCT, including Winnipeg, Halifax and Saint John. This includes both academic and non-academic cardiac surgery centers.
	
We plan to complete a Phase II, multicentre RCT examining the outcomes of patients undergoing Prehab during the patient journey from time of surgical referral to time of surgical procedure.
	
We plan to determine the cost effectiveness of the PREHAB model of care to determine if the intervention reduces different aspects of inpatient resource utilization .

Health Care System	We have completed a systematic review of current outcome(s) of frail elderly persons undergoing cardiac surgery and have determined that frailty is associated with increased mortality and other negative outcomes (see tables 1 & 2)	
Develop, Evaluate and Disseminate
 
 1. We have engaged local community cardiac rehabilitation programs in 3 provinces. 2. We have engaged a local regional health authority for study evaluation and developed an integrated knowledge translation plan (IKT) for patients/patient families, primary and specialist health care providers to ensure program sustainability 	
Improving care across the continuum:
 
We have already engaged and will continue to engage a national cardiac rehabilitation organization (CACR) to support our project through network development, patient advocacy, knowledge translation and knowledge transfer to the patients, their families and the inter-disciplinary healthcare teams involved in the care of the frail elderly person with cardiac disease.
	
Our long term plan is to access administrative data to determine if the Prehab intervention helps to reduce health care utilization for patients over a 1 and 5 year period. However, this aspect is a next stage beyond the scope of the current proposal.

“The PREHAB Study” (Pre-operative Rehabilitation for reduction of Hospitalization After coronary Bypass and valvular surgery.)

Table 2 - Characteristics of Included Studies In Frailty and Cardiac Surgery Systematic Review

First Author, Year	Population	n [#]	Frailty Measurement	Outcomes Measured	Association
Lee, 2010	Patients undergoing cardiac surgery	3826	Katz index of Activities of Daily Living (ADL), Independence in ambulation, and previous diagnosis of dementia	In-hospital mortality, midterm all-cause mortality, discharge to an institution, and secondary in-hospital outcomes	Frailty was linked to increased unadjusted In-Hospital Outcomes, increased In-hospital Mortality, increased institutional discharge, and reduced midterm survival
Singh, 2011	Patients ≥ 65 years undergoing Percutaneous Intervention	629	Fried Frailty Criteria	All cause mortality and MI during follow up	Frailty was an independent predictor of long-term mortality and MI
Sundermann, 2011	Patients ≥ 74 years undergoing cardiac surgery	400	Simplified Comprehensive Assessment of Frailty (CAF)	One year all cause mortality, and MACCE	Frailty showed a good predictive ability concerning one year mortality
Afilalo, 2012	Patients ≥ 70 years undergoing CABG and/or valve surgery	152	4 scales used: 5 item Cardiovascular Health Study (CHS) 7 item expanded CHS 4 item MacArthur Study of Successful Aging (MSSA)	Postoperative mortality or major morbidity Gait Speed	Only frailty measured through gait speed showed a statistically significant association with an increased mortality or major morbidity
Green, 2012	Patients ≥ 60 years with advanced aortic disease undergoing Transcatheter Aortic Valve Repair (TAVR)	159	Modified Fried Frailty Criteria	All cause mortality, and procedural outcomes	Frailty was independently associated with reduced long term survival after TAVR
Storteky, 2012	Patients ≥ 70 years undergoing Transcatheter Aortic Valve Implantation (TAVI)	100	Modified Multidimensional Geriatric Assessment	All cause mortality, and major adverse cardiac and cerebrovascular events (MACCE)	Strong evidence for an association between the frailty index with all cause mortality and MACCE at one year post-TAVI
Schoenenberger, 2013	Patients ≥ 70 years undergoing Transcatheter Aortic Valve Implantation (TAVI)	119	Modified Geriatric Baseline Examination	Functional decline, and functional decline or death	Frailty index was strongly associated with functional decline as well as mortality

Table 3 - Outcomes of Included Frailty and Cardiac Surgery Studies

First Author, Year	Association	
Lee, 2010	After Cardiac Surgery, Frailty is associated with In-Hospital Mortality	OR 1.8, 95% CI 1.1-3.0
	After Cardiac Surgery, Frailty is associated with Prolonged Institutional Care	OR 6.3, 95% CI 4.2-9.4
	After Cardiac Surgery, Frailty is associated with Mid-Term Mortality	HR 1.5, 95% CI 1.1-2.2
Singh, 2011	Frailty is associated with Death following Percutaneous Revascularization	HR 5.36, 95% CI 2.41-11.9
	Frailty is associated with MI/Death following Percutaneous Revascularization	HR 3.04, 95% CI 1.80-5.15
Sundermann, 2011	Frailty is associated with one-year mortality after cardiac surgery	OR 1.097, 95% CI 1.038-1.160
Afilalo, 2012	Frailty as measured through gait speed is associated with Mortality or Major Morbidity after CABG and/or valve surgery	OR 2.63, 95% CI 1.17-5.90
Green, 2012	Frailty is associated with increased one year mortality post TAVR	HR 3.16, 95% CI 1.33-7.51
Stortecky, 2012	Frailty is associated with increased all cause mortality one year post TAVI	OR 3.68, 95% CI 1.21-11.19
	Frailty is associated with increased MACCE one year post TAVI	OR 4.89, 95% CI 1.64-14.60
Schoenenberger, 2013	Post TAVI, Frailty is associated with functional decline	OR 3.31, 95% CI 1.21-9.03
	Post TAVI, Frailty is associated functional decline or death	OR 4.46, 95%CI 1.85-10.75

ADL, Activities of Daily Living; MI, Myocardial Infarction; CAF, Comprehensive Assessment of Frailty; MACCE, Major Adverse Cardiac and Cerebrovascular Events; CABG, Coronary Artery Bypass Graft; CHS, Cardiovascular Health Study; MSSA, MacArthur Study of Successful Aging; TAVR, Trans-catheter Aortic Valve Repair; TAVI, Trans-catheter Aortic Valve Implantation; BMI, Body Mass Index; MMSE, Mini Mental State Exam; MNA, Mini Nutritional Assessment; TUG, Timed Get Up and Go test; BADL, Basic Activities of Daily Living; IADL, Instrumental Activities of Daily Living

* study sample size

Table 4 - Characteristics of “not frail” versus “frail” patients, according to the Modified Fried definition of frailty

Pre-Operative Characteristics	Not Frail (N=61)	Frail (N=72)	P-Value
Age (years)	68.7 (7.4)	73.0 (8.2)	0.0023
Female sex	11 (18.0%)	24 (33.3%)	0.0459
BMI (kg/m²)	29.0 (6.0)	29.3 (5.8)	0.8079
Diabetes	13 (21.3%)	29 (40.3%)	0.0190
HbA1c (%)	5.9 (5.7 – 6.6)	6.1 (5.9 – 7.1)	0.2312
CVD	4 (6.6%)	15 (20.8%)	0.0191
COPD	1 (1.6%)	15 (20.8%)	0.0008
Clinical depression	5 (8.2%)	10 (13.9%)	0.3011
Arthritis	5 (8.2%)	17 (23.6%)	0.0171
Angina	37 (61.7%)	50 (69.4%)	0.3479
Smoking history	39 (63.9%)	44 (62.0%)	0.8160
Current smoker	1 (1.6%)	5 (7.0%)	0.2162
Anemia	9 (14.8%)	22 (30.6%)	0.0317
Albumin (g/L)	39.0 (3.1)	36.4 (4.5)	0.0011
Chronic renal failure	0 (0.0%)	4 (5.6%)	0.1245
Creatinine (μmol/L)	90 (76 – 100)	85 (71 – 116)	0.8231
GI disease	14 (23.0%)	27 (37.5%)	0.0702
PVD	4 (6.6%)	13 (18.1%)	0.0478
Dyslipidemia	40 (65.6%)	51 (70.8%)	0.5155
Pulmonary hypertension	2 (3.3%)	4 (5.6%)	0.6870
Hypertension	48 (78.7%)	65 (90.3%)	0.0624
CHF	30 (49.2%)	40 (55.6%)	0.4631
MI	20 (32.8%)	31 (43.1%)	0.2249
Atrial fibrillation	7 (11.5%)	15 (20.8%)	0.1478
Prior angioplasty or stent	5 (8.2%)	18 (25.0%)	0.0107
Prior cardiac surgery	4 (6.6%)	2 (2.8%)	0.4124
Visual impairment	17 (27.9%)	19 (26.4%)	0.8482
Hearing impairment	3 (4.9%)	5 (6.9%)	0.7260
EuroSCORE II (%)	1.42 (0.87 – 1.94)	2.02 (1.25 – 4.28)	0.0001
Self-health rating (0-4)	3 (2 – 3)	2 (1 – 2)	<0.0001
MoCA score (0-30)	26 (24 – 27)	22 (20 – 25)	<0.0001

“The PREHAB Study” (Pre-operative Rehabilitation for reduction of Hospitalization After coronary Bypass and valvular surgery.)

Table 5 - Intraoperative Variables

Intra-Operative Characteristics	Not Frail (n=61)	Frail (n=72)	P-Value	OR (95% CI)
Procedure type			0.5729	
- Isolated CABG	26 (42.6%)	39 (54.2%)		
- Isolated Valve	19 (31.2%)	17 (23.6%)		
- CABG + Valve	12 (16.7%)	13 (18.1%)		
- Other	4 (6.6%)	3 (4.2%)		
CPB time (minutes)	102 (80 – 132)	89 (68 – 121)	0.1712	

Table 6 - Unadjusted Association of Frailty and Risk of Negative Postoperative Outcome

Post-Operative Outcomes	Not Frail (n=61)	Frail (n=72)	P-Value	OR (95% CI)
ICU LOS (days)	2 (1 – 3)	2 (1 – 3)	0.2819	
Hospital LOS (days)	6 (5 – 9)	8 (6 – 12)	0.0098	
ICU LOS > 72 hours	10 (16.4%)	17 (23.6%)	0.3025	1.58 (0.66 – 3.76)
Hospital LOS > 7 days	23 (37.7%)	42 (58.3%)	0.0177	2.31 (1.15 – 4.65)
Major adverse event	1 (1.6%)	4 (5.6%)	0.3742	3.52 (0.38 – 32.45)
Post-operative Delirium	4 (6.6%)	20 (27.8%)	0.0015	5.48 (1.76 – 17.09)
In-hospital mortality	0 (0.0%)	2 (2.8%)	0.4997	undefined
Discharge to Institution	1 (1.6%)	4 (5.6%)	0.3713	3.64 (0.40 – 33.45)

Categorical variables are listed as frequency values (%), continuous variables are listed as mean (standard deviation) or median (interquartile range). Statistical comparisons were calculated using Chi-Square or Fisher Exact Test for categorical variables, T-Test or Mann-Whitney Test for continuous variables.

Table 7 - Comparison of baseline data between Standard care and Prehab groups

	Standard care (n= 7)	Prehab (n= 7)	P-value
Demographics			
Age (years)	63 ± 3	64 ± 4	0.63
Gender (% female per group)	1 (14%)	2 (25%)	0.99
Height (cm)	172.6 ± 2.3	173.0 ± 4.1	0.79
Weight (kg)	89.4 ± 2.4	94.1 ± 5.5	0.46
BMI	30.0 ± 1.0	29.9 ± 1.2	0.43
Pre-operative Characteristics			
Ejection fraction	$62\% \pm 4\%$	$58\% \pm 4\%$	0.51
CCS class	2.4 ± 0.2	2.4 ± 0.4	1.00
Previous MI	4 (57%)	4 (50%)	1.00
Arrhythmia	3 (43%)	2 (25%)	1.00
Hypertension	6 (86%)	6 (75%)	1.00
CVA/TIA	1 (14%)	1 (13%)	1.00
Psychiatric Diagnosis	2 (29%)	1 (13%)	1.00
Diabetes	1 (14%)	3 (38%)	1.00
Hyperlipidemia	7 (100%)	6 (75%)	1.00
Medications			
Beta-blocker	7 (100%)	2 (25%)	0.02
ACE/ARB	4 (57%)	3 (75%)	1.00
Statin	7 (100%)	7 (88%)	1.00
Anti-platelet	3 (43%)	2 (25%)	1.00
Nitrate	5 (71%)	4 (50%)	1.00
Anti-depressant	2 (29%)	0 (0%)	0.46

Continuous variables expressed as mean \pm standard error. Categorical variables expressed in frequencies (percentage of group).

CCS= Canadian cardiovascular society angina score; MI= myocardial infarction; CVA= cerebrovascular accident; TIA= transient ischemic attack; ARB= angiotensin receptor blocker; ACE= angiotensin converting enzyme.

“The PREHAB Study” (Pre-operative Rehabilitation for reduction of Hospitalization After coronary Bypass and valvular surgery.)

Table 8 - Comparison of operative characteristics between Standard care and *Prehab* groups

	Standard care (n= 7)	Pre-Hab (n= 7)	P-value
Time on wait list (days)	66 ± 6	92 ± 19	0.46
2-3x CABG	5 (71%)	5 (63%)	0.99
4-5x CABG	2 (29%)	3 (38%)	0.99
Cardiopulmonary bypass time (minutes)	69 ± 18	67 ± 6	0.92
ICU length of stay (hours)	25 ± 3	24 ± 4	0.80
Length of hospital stay (days)	5.3 ± 0.4	5.1 ± 0.5	0.81

Continuous variables expressed as mean ± standard error. Categorical variables expressed in frequencies (percentage of group). CABG = coronary artery bypass graft; ICU = intensive care unit.

Table 9 – Comparison of physical activity as measured by accelerometry between the Standard care and *Prehab* groups at baseline and Postop

	Baseline	Postop	ANOVA p-values		
			Group	Time	Interaction
10 minute bouts					
MVPA_{10min}			0.62	0.10	0.44
- Standard care	82 ± 58	130 ± 51			
- Prehab	21 ± 15	147 ± 53			
TotalPA_{10min}			0.49	0.07	0.56
- Standard care	103 ± 66	198 ± 89			
- Prehab	23 ± 150	193 ± 65			
Sporadic bouts					
MVPA_{spor}			0.87	0.03	0.73
- Standard care	132 ± 64	281 ± 72			
- Prehab	139 ± 64	250 ± 53			
TotalPA_{spor}			0.66	0.10	0.75
- Standard care	576 ± 89	872 ± 197			
- Prehab	574 ± 100	780 ± 84			

Values are means ± standard error; Standard care n= 6; *Prehab* n= 7. MVPA= moderate to vigorous physical activity.

“The PREHAB Study” (Pre-operative Rehabilitation for reduction of Hospitalization After coronary Bypass and valvular surgery.)

Table 9 - Seven step Formative Evaluation Plan

Aspects of the Implementation Process	Evaluation Component	Description of the evaluation component at different levels	Data collection method(s)
Adoption	Recruitment	Site level : [primary care practice & specialist(s)]: Procedures used to approach and attract sites Patient level : Procedures used to approach patients for participation in pre-operative rehabilitation	Observation Questionnaire, interview
Implementation	Reach	Site level : proportion of different sites approached and then accepting contribution to the study Patient level : proportion of patients approached and then participating in the intervention	Monitoring
	Effectiveness	Site & Project levels : Proportion of primary care sites and specialists who delivered (project level) and received (site level) the 7-step strategy	Monitoring, questionnaires, interviews
	Fidelity	Project group : extent to which the 7-step strategy was adhered to and adherence to the project's implementation plan	Monitoring, questionnaires, interviews
	Satisfaction	Site level : opinion/satisfaction about the study and intervention Project level : opinion/satisfaction about the 7-step strategy Patient level : opinion/satisfaction about the pre-operative rehabilitation strategy	Questionnaires, interviews
Continuation	Maintenance	Site level : the extent to which pre-operative rehabilitation becomes routine and a part of everyday culture and norms practices.	Monitoring, questionnaires, interviews
Implementation Determinants	Context	Determinants of implementation which have either hindered or facilitated the use of the 7-step strategy and pre-operative rehabilitation intervention. Specifically, we will examine the characteristics of the (a) socio-political context (e.g., willingness to be involved), (b) organization (e.g., decision making processes, capacity, financial resources), (c) adopting practices/patients (e.g., self-efficacy, support from colleagues/family, benefits), and (d) intervention (e.g., clarity of process)	Monitoring, questionnaires, interviews

"The PREHAB Study" (Pre-operative Rehabilitation for reduction of Hospitalization After coronary Bypass and valvular surgery.)

Figures

Case example:

Appendix I - Modified Fried Criteria (1-7)

Frailty Domain	Method of Measurement	Cutoffs for Measurement
1 Slowness	4-meter gait speed Measures the time required to walk 4 meters at a normal pace (use the best of two times)	<4.82 sec: 4 pt 4.82-6.20 sec: 3 pt 6.21-8.70 sec: 2 pt >8.7 sec: 1 pt Unable: 0 pt
2 Weakness	Handgrip strength The patient is asked to squeeze the handgrip dynamometer as hard as possible, this is repeated 3 times (with each hand and then with the strongest hand) and the maximum value is recorded	Sex- and BSA-based cutoff ♂: ≤24 kg/m ² : ≤29 kg 24.1-28 kg/m ² : ≤30 kg ♂: >28 kg/m ² : ≤32 kg ♀: ≤26 kg/m ² : ≤17 kg 26.1-29 kg/m ² : ≤18 kg ♀: >29 kg/m ² : ≤21 kg Simplified cutoff ♂: ≤30 kg ♀: ≤20 kg
3 Low physical activity	PASE & Paffenbarger Physical Activity Questionnaire	♂: <383 kcal/week ♀: <270 kcal/week
4 Weight loss	Self-reported	>10 pounds or >5% in past year
5 Exhaustion	a) 2 questions from CES-D: How often in the last week did you feel this way: i. I felt that everything was an effort ii. I could not get going	Positive if answered either question Most of the time or Moderate amount of the time
6 Cognitive impairment	Montreal Cognitive Assessment (MoCA) Trails A and B	Score <26/30
7 Depressed mood	Geriatric depression scale (5-item)	Score ≥2/5
≥3 Criteria Required for Diagnosis of Frailty		

“The PREHAB Study” (Pre-operative Rehabilitation for reduction of Hospitalization After coronary Bypass and valvular surgery.)

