3.1.1.1 Frailty in the Cardiac Surgery Population at St. Boniface Hospital

We undertook a systematic review of frailty in the elderly undergoing cardiac surgery (see *Table 2 & Table 3*).(23)(24)(25)(26)(27)(28)(29)(30)(31) This review demonstrated an association with increased frailty and a major negative outcomes ranging from increased institutional care to major adverse cardiac and cerebral event (*MACCE*) and increased in-hospital and long-term mortality after cardiac surgery. However, the lack of a standardized and comprehensive definition of frailty in these studies prevents clarity in understanding the interaction of frailty in the elderly and cardiac surgery. We subsequently completed a prospective examination of frailty in 133 consecutively consenting elderly cardiac surgery patients with high-levels of co-morbid disease (See *Table 4*, *Table 5*, *Table 6* and *Figure 2*). Two definitions of frailty were used (see *Appendix I*): (1) *Modified Fried criteria*: (32)(33)(34) a patient was deemed “frail” if they met ≥ 3 of the following 7 criteria: slowness (5m gait speed)(35), weakness (handgrip strength measurement)(36) and questionnaires assessing self-reported weight loss, exhaustion (the two-item Center for Epidemiologic Studies Depression (*CES-D Scale*), depression (the 5-point geriatric depression scale (*5-GDS*))(37)(38)), low physical activity (the Paffenbarger Physical Activity Index(39)(40)(41)(42)), and cognitive impairment (the Montreal Cognitive Assessment (*MoCA*))(43)(44)(45)). (2) *Short Physical Performance Battery (SPPB)*: a patient was deemed “frail” if his/her composite score was ≤ 9 based on 5m gait speed, balance tests, and the repeated chair stand test (each scored from 0 to 4)(46). Using the modified Fried or the SPPB criteria, 72 (54.1%) or 69 (51.9%) (respectively), patients studied were deemed frail (See *Table 3*). Frail patients were older, more commonly female, had higher *EuroSCORE II* values (a cardiac surgery specific mortality risk prediction score) and lower self-health ratings. Diabetes, cerebrovascular disease (*CVD*), chronic obstructive pulmonary disease (*COPD*), arthritis, anemia, peripheral vascular disease (*PVD*), and lower serum albumin were also significantly associated with being frail. Notably, frailty correlated with clinically important measures of increased hospital *LOS*: total adjusted hospital *LOS* (median 6 days (IQR: 5 – 9) in non-frail vs. 8 days (IQR 6 – 12) in “frail” patients, $p < 0.001$) and a greater proportion of patients in hospital > 7 days (37.7% in non-frail vs. 58.3% in frail patients, $p < 0.02$; See *Table 4 & Table 5*). This longer hospital stay amongst frail patients has implications for increased healthcare costs and we have observed an association between new and persistent mood disorders and reduced engagement in postoperative physical activity with a hospital *LOS* > 7 days after cardiac surgery.

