3.4.2 Frailty Assessments

Our strategy for rapid screening of frailty in a large volume of clinic patients will be to use the 9-point Clinical Frailty Scale (*CFS*) (56)(See *Figure 4* and appendix). The *CFS* is the simplest tool to implement at multiple centres, has a high inter-observer reliability and shows good performance (by *ROC analysis*) for risk of death or institutionalization. Due to the need to screen a large number of individuals (785 patients; *Figure 5*) the use of the *Modified* and *SPPB* are less practical to implement as routine practice in the outpatient clinic sites. Therefore our approach is to use a *CFS* score of ≥ 3 as the initial indication of frailty (57) . This approach will allow us to estimate degrees of frailty in a large volume of patients in a rapid, cost-effective and highly feasible manner. All enrolled patients will be further assessed using the modified Fried criteria(33)(32)(34), and a reduction of frailty will be defined as a binary value (i.e. frail/non-frail) using these criteria(33)(32)(34).

The *SPPB* criteria will be used as a third measure.(46) As a fourth measure, our data collection protocol will also enable a Frailty Index (*FI*) calculation.(29)(56)(58)(30) The inclusion of the more definitive frailty evaluations are intended to gain more information about the different domains of frailty in the elderly to further improve the clinical frailty assessments that will be used in the future. To ensure reliability of this approach, we have compared the three measures of frailty (*CFS*, *Modified* and *SPPB*) on 169 elective cardiac surgery patients at the St. Boniface Hospital. The spearman correlation was ~ 0.65 for all three comparisons and the Cohen’s Kappa, which is a concordance measure between the different frailty definitions is ~ 0.50 . These values indicate a moderately strong link between all three measures; however it is possible that they capture somewhat different domains of frailty.

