3.5.2 Safety and Baseline Assessments

A medical director, at each site, will oversee all cases and ensure patient eligibility and safety for program initiation and throughout program attendance for the study duration. All eligible and consented patients will be evaluated at baseline to ensure angina stability. Exercise prescription will be determined utilizing the standard practice of the Karvonen Equation adjusted according to pre-program exercise stress test. (21)Patients will also undergo a standard *6MWT* (73)(74)(75)(76)(77)(78) and will repeat the *6MWT* at the preoperative time point in both the control and *Prehab* groups to determine impact of the intervention. The *6MWT* was chosen because it requires minimal infrastructure and personnel to complete and has been demonstrated to be a valid prognostic tool for patient outcomes and is comparable to an exercise-stress test. (73)(75)(76)(77)This approach enables us to avoid potential scheduling issues that occur if a patient’s surgical date is moved up.

Patients who are deemed appropriate for enrolment into study will be randomized, following the completion of the baseline data collection, to one of two trial arms – control (standard of care (*StandC*) or treatment (*Prehab*). Baseline risk factor evaluation, anthropometrics, clinical markers, patient questionnaires (including frailty scores, cognitive assessment, and quality of life data) and physical activity data measured using accelerometers will be collected for all patients and repeated pre-operatively and at three-month follow up. Safety data including new hospitalization, worsening angina or heart failure and arrhythmias will be captured and all adverse events will be reportable to the study Data Safety Monitoring Board (*DSMB*). All patients in both groups will be referred to postoperative *CR* programming, as per local practice.

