3.5.5.5 Health behavior interventions and risk factor modification

PREHAB patients all receive a comprehensive, multi-faceted health behavior intervention with the goal of positively modifying their risk factor profile. This includes nutritional counseling, lipid management, hypertension management, smoking cessation, weight management, diabetes management, adherence to prescribed pharmacotherapy, psychosocial management, and physical activity counseling.

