5.2 Statistical/Analytical Plan

Objective 1: To determine if *Prehab* reduces the proportion of frail elderly patients requiring a prolonged hospital length of stay of >7 days. A univariable analysis will be undertaken to determine if hospital *LOS* > 7 days is associated with frailty and other patient-level factors. A stepwise multivariable logistic regression model will then be developed to determine if *Prehab* attendance is independently associated with a decreased risk of prolonged hospital length of stay > 7 days. As a secondary analysis, hospital *LOS* will also be compared as a continuous variable between the *Prehab* and standard care groups using a Mann-Whitney test.

“The PREHAB Study” (Pre-operative Rehabilitation for reduction of Hospitalization After coronary Bypass and valvular surgery.)

Objective 2: Does attending *Prehab* influence frailty, exercise capacity, physical activity behavior, in-hospital complications, and *HRQoL*? Although we will employ four different measures of frailty, based on our preliminary data and based on a Task Force’s position statement(90), the Modified Fried Criteria will be the primary frailty outcome over time from baseline to the end of *Prehab* program (pre-operatively), or from baseline to the 3-month post-operative follow-up. The primary measure of exercise capacity will be the *6MWT* and will be analysed with univariable linear regression models to evaluate the association between the *6MWT* and *Prehab* attendance. Accelerometers will be used to objectively measure the number of minutes spent performing moderate to vigorous physical activity (*MVPA*) and total physical activity (*TPA*) per day for a period of 7 days and compared between groups. A composite outcome for a major adverse cardiac event (i.e. *MACCE* = in-hospital stroke, myocardial infarction, renal failure requiring dialysis and death) and delirium will be compared between groups using a Chi-Square or Fisher’s Exact test. A multivariable logistic regression will be used to identify if *Prehab* is independently associated with in-hospital delirium. The *SF-12v2* and *EQ-5D* scores, after normative standardization, will be analyzed through use of a repeated *ANOVA* to allow for a standardized group and group/time interaction effect estimation.

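### The weight-loss item of the Modified Fried criteria is not limited to unintentional loss, so deliberate loss can add a frailty criterion more often in the Prehab arm, which receives weight management

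*Combined protocol and SAP*

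**What the plan says.** Appendix I lists seven Modified Fried criteria. Item 4, weight loss, is self-reported and positive at ">10 pounds or >5% in past year". Nothing in the row refers to intent. Section 3.1.1.1, which describes the same criteria, adds no condition either: it mentions "questionnaires assessing self-reported weight loss, exhaustion" and moves on. Section 3.4.8 names a Nutrition/Exhaustion Questionnaire that probably carries the item, but its wording is not reproduced.

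The frailty cut-off is "≥3 Criteria Required for Diagnosis of Frailty". Section 3.4.2 states that "a reduction of frailty will be defined as a binary value (i.e. frail/non-frail) using these criteria", and Section 5.2 that "the Modified Fried Criteria will be the primary frailty outcome over time", from baseline to the pre-operative visit or to 3 months after surgery. Frailty is the first of the secondary outcomes in Section 5.1.2.

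Section 3.5.5.5 describes what every Prehab patient receives: "This includes nutritional counseling, lipid management, hypertension management, smoking cessation, weight management, diabetes management", among other components. Section 3.5.5.4.4 adds a dietitian visit based on a 3-day food recall. In standard care (Section 3.5.4), a cardiac nurse counsels each patient on behaviours such as diet and exercise. Section 3.5.2 has "Baseline risk factor evaluation, anthropometrics, clinical markers, patient questionnaires" collected at baseline and repeated pre-operatively and at 3 months.

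**The concern.** An outcome measure should not count an intended effect of the tested intervention as a sign of the condition being treated. Here it can. The cohorts in the protocol are overweight on average (mean BMI 29.0 and 29.3 in Table 4; 30.0 and 31.5 in the pilot report), so deliberate weight loss is a plausible result of the Prehab package. A Prehab patient who loses enough weight on purpose gains one of the seven criteria.

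Because the weight-related input is heavier in one arm, the misclassification would be differential and would run against Prehab. It could mask improvement: a patient who enters with three criteria, resolves one and newly triggers item 4 is still scored frail. At stake is the secondary comparison closest to the trial's stated aim of reducing frailty before surgery.

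**Working it through.** **The plan's own figures.** The sample size rests on length of stay and reproduces. With p1 = 0.583, p2 = 0.383 and mean 0.483, n = [1.96·√(2·0.483·0.517) + 0.8416·√(0.583·0.417 + 0.383·0.617)]² / 0.20² = 96.8, so 97 per arm. Then 97/0.8 = 121.25, so 122 per arm and 244 in total. Nothing here depends on item 4. The plan gives no figure for weight change. The only usable frailty figure is 72/133 = 54.1% frail by Modified Fried in the preliminary cohort (Section 3.1.1.1).

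**How much loss triggers item 4.** The trigger is the lower of 10 lb (4.54 kg) and 5% of body weight. The two are equal at 4.54/0.05 = 90.7 kg. The two heaviest example weights are the pilot means (standard care 89.4 kg, Prehab 94.1 kg); 70 and 80 kg are illustrative.

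| Weight | Trigger | Over 4 weeks | Over 8 weeks |
|---|---|---|---|
| 70 kg | 3.5 kg | 0.88 kg/wk | 0.44 kg/wk |
| 80 kg | 4.0 kg | 1.00 kg/wk | 0.50 kg/wk |
| 89.4 kg | 4.47 kg | 1.12 kg/wk | 0.56 kg/wk |
| 94.1 kg | 4.54 kg | 1.13 kg/wk | 0.57 kg/wk |

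These rates assume no earlier loss in the look-back year; earlier loss lowers the amount needed. For the 3-month assessment, 4-8 weeks of programme plus about 12 weeks gives 16-20 weeks, and the rate falls to between 3.5/20 = 0.18 and 4.54/16 = 0.28 kg/week.

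**Who changes status.** One extra item turns non-frail into frail only if exactly two of the other six are positive. Assume independent items, equal prevalence q for the other six, and prevalence w for item 4. Choose q so that P(3 or more of 7) = 0.541.

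- w = 0.10 gives q = 0.427 and P(exactly 2 of 6) = 15·0.427²·0.573⁴ = 0.295.
- w = 0.20 gives q = 0.412 and P(exactly 2 of 6) = 15·0.412²·0.588⁴ = 0.304.

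Under these assumptions the share peaks at q = 1/3, where it is 15·(1/3)²·(2/3)⁴ = 0.329. A different frailty prevalence would therefore not raise it much.

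**Shift in the frail proportion.** Shift = (excess share newly positive on item 4 in Prehab) × (about 0.30).

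| Assumed excess | Shift |
|---|---|
| 2% | 0.6 points |
| 5% | 1.5 points |
| 10% | 3.0 points |
| 20% | 6.0 points |

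Without the independence assumption, the shift still cannot exceed the excess share itself.

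**Look-back overlap.** The share of the one-year window common to baseline and a later visit is 1 − weeks/52: 92% at 4 weeks, 85% at 8, 77% at 12 (the Manitoba median wait in Section 3.5.6), and 69-62% at 16-20. The item therefore responds slowly to recovery, in both arms.

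**The case against.** Several stronger readings are tempting, and the documents do not support them.

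- **The item counts deliberate loss by design.** This is inferred from silence. The questionnaire wording is not shown and may already ask about intent. What stands is that the written scoring rule does not.
- **A patient who responds to Prehab is scored as more frail.** This follows only if loss passes the threshold and the item was not already positive, and frail status changes only if exactly two other items are positive. Better gait, grip, activity or mood moves the count the other way; pilot gait speed improved by 27% pre-operatively. An apparent worsening of frailty is not shown.
- **The programme asks patients to lose weight.** No weight-loss target is set. Weight management is one of nine listed components, and the dietitian's stated purpose is to optimise diet.
- **The bias exists in one arm only.** Controls also receive counselling on diet and exercise, although lightly. Both arms are referred to post-operative rehabilitation, in which 43% of pilot controls enrolled against 100% of Prehab patients. The contrast is one of degree.
- **The look-back lets the item only add positives.** Older loss can leave the window and weight can be regained. The overlap applies to both arms, so it is not itself a differential bias.

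It is also fair to say that three other frailty measures are collected, and that the SPPB (gait, balance, chair stands) has no weight component and offers an independent check. These points limit the size of the problem. They leave in place a scoring rule for the main frailty measure that can count an intended effect of the intervention, more often in one arm.

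**Conclusion.** The point holds in a limited form. As written, item 4 can count deliberate loss, and the Prehab arm is more exposed to causes of such loss. The resulting bias runs against Prehab and is probably small: about 1.5-3 points in the frail proportion if an assumed 5-10% of Prehab patients cross the threshold in excess of controls. That figure rests on independent items, equal prevalence among the other six, calibration to 54.1% frail, and an assumed crossing rate; the documents contain no weight-change data to test it. The effect is confined to a secondary outcome. Length of stay and the sample size are untouched. The change is worth making because it is cheap and corrects a stated rule.

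**What to change.** 1. In Appendix I, define item 4 as unintentional loss of the stated amount, in wording that names no arm-specific exposure, for example *without trying to lose weight*. Make the Nutrition/Exhaustion Questionnaire match if it does not already. Avoid a list such as dieting, exercise or counselling: it would prompt Prehab patients to attribute illness-related loss to the programme and be scored negative, while the same loss in a control would count.
2. Ask the question identically in both arms at every visit at which the criteria are scored.
3. Check the amount against weight from the anthropometrics already repeated pre-operatively and at 3 months, assuming these include weight. This verifies loss since baseline, not loss in the year before entry.
4. Add to Section 5.2 a sensitivity analysis of frailty that omits item 4 in both arms, and state its cut-off. With three or more of the remaining six, the illustrative frail proportion becomes 0.541 − 0.10·0.295 = 51% or 0.541 − 0.20·0.304 = 48%. The definition is somewhat stricter but the same in both arms.

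The cost is one line in the appendix, one question on an existing form and one extra analysis, with no new visit or measurement. The downside is that reported intent in an open-label trial may be attributed differently by arm. The analysis without item 4 does not depend on reported intent and so addresses this. The rewording does not remove the slow response caused by the one-year look-back.
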